2.3 Benefit/Risk Assessment

This trial is designed primarily to evaluate the efficacy and safety of 2 fixed doses (15 mg QD and 30 mg QD) of emraclidine in the target patient population.

Based on results from Part B of Trial CVL-231-SCH-001, treatment with 30 mg QD emraclidine in patients with schizophrenia experiencing an acute exacerbation of psychosis may be beneficial based on clinically meaningful reductions from Baseline in PANSS and CGI-S scores (see [Section 2.2.3](#)).

Doses were chosen for this trial based on nonclinical safety and toxicology data and clinical safety data available to date (see [Section 4.3](#)).

There is a potential for an increase in blood pressure and heart rate based on nonclinical findings and findings from the single and multiple ascending dose trials (see [Section 2.2.2](#) and [Section 2.2.3](#)). The cardiovascular effects of emraclidine will be carefully monitored on an inpatient basis throughout the trial. The inpatient design will also facilitate careful monitoring of participants during and subsequent to washout from their antipsychotic drug treatment.

More detailed information about the known and expected benefits and potential risks of emraclidine are found in the Investigator's Brochure.

3 OBJECTIVES AND ENDPOINTS

Table 2 Objectives and Endpoints

Objectives	Endpoints
Primary	
Primary Endpoint:
 
 • Change from Baseline at Week 6 in the PANSS total score 
Key Secondary Endpoint:
 
 • Change from Baseline at Week 6 in the CGI-S score 
Secondary Endpoints:
 
 • Change from Baseline at all time points in PANSS total score • Change from Baseline at all time points in CGI-S score • Percentage of responders at Week 6 (responders defined as $\geq 30\%$ reduction from Baseline in PANSS total score) 
Exploratory Endpoints:
 
 • CGI-I at Weeks 3 and 6 • Change from Baseline at all time points in PANSS positive, negative, and general psychopathology subscale scores • Change from Baseline at all time points in PANSS Marder Factor scores
Secondary	
 • Treatment-emergent adverse events • Clinically significant changes in electrocardiograms, clinical laboratory assessments and metabolic parameters, standard vital sign measurements, and physical and neurological examination results, including body weight • Clinically significant findings in suicidality assessed using the C-SSRS • Extrapyramidal symptoms evaluated using the change from Baseline in SAS, AIMS, and BARS assessments

Objectives	Endpoints
Exploratory	

 To evaluate the plasma pharmacokinetics of emraclidine and its metabolite, CV-0000364, following 2 fixed oral doses (15 mg QD and 30 mg QD) of emraclidine in adult participants with schizophrenia experiencing an acute exacerbation of psychosis 	
 Pharmacokinetic parameters for emraclidine and its metabolite, CV-0000364 (C_{max} and AUC_{tau})

 To evaluate quality of life and cognition following 2 fixed oral doses (15 mg QD and 30 mg QD) of emraclidine in adult participants with schizophrenia experiencing an acute exacerbation of psychosis 	
 Change from Baseline at Week 6 in BACS symbol coding test Change from Baseline at Week 6 in SF-6D

Abbreviations: AIMS=Abnormal Involuntary Movement Scale; AUC=area under the concentration-time curve; BACS=Brief Assessment of Cognition in Schizophrenia; BARS=Barnes Akathisia Rating Scale; CGI-I=Clinical Global Impression-Improvement of Symptoms; CGI-S=Clinical Global Impression-Severity of Symptoms; C_{max} =maximum (peak) plasma concentration; C-SSRS=Columbia-Suicide Severity Rating Scale; PANSS=Positive and Negative Syndrome Scale; QD=once daily; SAS=Simpson Angus Scale; SF-6D=Short Form-6 Dimensions.

4 TRIAL DESIGN

4.1 Overall Design

This is a Phase 2, multicenter, randomized, double-blind, placebo-controlled, parallel-group, 6-week trial to evaluate the efficacy, safety, and tolerability of 2 fixed doses of emraclidine (15 mg QD and 30 mg QD) in male and female participants aged 18 to 65 years, inclusive, who have schizophrenia and are experiencing an acute exacerbation of psychosis. The trial will include up to a 15-day Screening Period (up to a maximum of 21 days allowed with approval of the medical monitor), a 45-day Inpatient Treatment Period, and a 28-day Follow-up Period. Each participant will participate in the trial for up to approximately 13 weeks.

4.1.1 Screening Period

Participants will enter a Screening Period up to 15 days (up to a maximum of 21 days allowed with approval of the medical monitor) to assess eligibility criteria and washout from prior antipsychotic medications and other prohibited medications. All participants will be admitted to the inpatient facility at the time they sign the ICF and remain in the inpatient facility for the duration of treatment.

Approximately 600 participants will be screened to achieve approximately 372 participants qualified to be randomized to treatment in the trial.

4.1.2 Treatment Period

On Day 1 (Baseline), participants will be randomized in a 1:1:1 ratio to the following treatment groups with approximately 124 participants per treatment group:

- Emraclidine 15 mg QD
- Emraclidine 30 mg QD
- Placebo QD

The randomization will be stratified by geographic region with 2 strata: United States or all other countries.

The daily dosing schedule will start on Day 1 with all participants receiving a single daily dose of IMP in the morning.

Participants are to remain in the inpatient facility for the entire duration of the trial (ie, from ICF signing through Week 6/ET); however, beginning at the Week 3 time point, participants who are sufficiently stable (per investigator assessment) may receive day passes for urgent issues. While away from the site, participants must be supervised by hospital/research staff (medical monitor approval for supervision by a family member or caregiver may be obtained). Participants are not permitted to stay away from the inpatient facility overnight; if, in unforeseen circumstances, the participant is unable to return to the facility the same day, the medical monitor should be contacted to discuss continuing participant eligibility. In addition, the participant must agree to submit to testing (ie, urine drug screen and alcohol breathalyzer test) upon return to the site. If the breathalyzer test is positive, the medical monitor should be contacted to determine the continued eligibility of the participant. Participants returning from a day pass who have a positive urine drug screen should be discontinued from the trial. However, if the positive urine drug screen results from use of marijuana (any THC-containing product), prescription, or over-the-counter medications or products that, in the investigator's documented opinion, does not signal a clinical condition that would impact the safety of the participant or interpretation of the trial results, the participant may continue in the trial following consultation and approval by the medical monitor.

All participants will continue dosing through Day 45 of Week 6. For the Week 6 time point, trial assessments will be completed on 2 separate days; on Day 42, the PANSS, CGI-S, and CGI-I will be completed, and on the last day of the treatment period, Day 45, the remaining scale and safety assessments will be completed. A minimum of 3 days is required between the completion of the Day 42 assessments and the Day 45 assessments, as noted in the Schedule of Assessments ([Table 1](#)). Participants will receive their last dose of IMP on Day 45.

Participants who complete all trial visits, through Week 6 (Day 45), may be offered entry into an optional open-label rollover trial when the trial has been initiated for rollover participation.

4.1.3 Follow-up Period

All participants (completers and early withdrawals), with the exception of those entering the optional open-label rollover trial, will have a follow-up safety contact at approximately 28 days after the last dose of IMP.

Participants may be allowed to stay in the inpatient facility up to 7 days after their last dose of IMP if necessary to achieve stabilization on alternate therapy with review and approval by the medical monitor.

4.1.4 Definition of Completed Participant

A participant is considered to have completed the trial if he/she has completed the inpatient Treatment Period of the trial including the last inpatient visit (Day 45), as shown in the Schedule of Assessments in [Section 1.3](#).

4.2 Scientific Rationale for Trial Design

The randomized, double-blind, placebo-controlled, parallel-group trial design minimizes the risk of bias and is considered appropriate for evaluating the effects of a trial treatment for indications in which use of a placebo is ethical ([US FDA, 2001](#)). Randomization reduces bias in the assignment of participants to a treatment group, the double-blind design prevents differential treatment and assessments, and the placebo-controlled design controls for all potential influences on the actual or apparent course of the disease other than those arising from the pharmacologic action of the drug.

The 6-week duration of the current trial is of sufficient length to show a treatment effect on acute exacerbation of schizophrenia symptoms and has been used for prior trials of antipsychotics evaluated to treat acute psychotic symptoms in patients with schizophrenia ([Correll et al, 2020](#); [Correll et al, 2016](#); [Leucht et al, 2013](#); [McEvoy et al, 2007](#); [Kane et al, 2015](#)). As described in [Section 2.2.3](#), emraclidine 30 mg QD demonstrated antipsychotic activity compared with placebo in Part B of Trial CVL-231-SCH-001 based on assessment of PANSS total score and CGI-S score at 6 weeks.

The PANSS is a widely used and validated measure of the severity of core positive and negative symptoms associated with schizophrenia, as defined by the DSM-5. The change from Baseline in the PANSS total score has been the basis of approval for many antipsychotic agents, including Latuda, Rexulti, and Caplyta ([Latuda Package Insert, 2013](#); [Rexulti Package Insert, 2018](#); [Caplyta Package Insert, 2019](#)). The CGI-S, which is also widely used and accepted, is included as a supplementary scale to provide a global assessment of clinical status. The BACS is a highly sensitive measure of cognitive defects in patients with schizophrenia; the symbol coding test of the BACS is included in the trial to evaluate the potential effect of emraclidine on attention and processing speed ([Keefe et al, 2004](#); [Dickinson et al, 2007](#)).

The safety assessments, including those for assessing EPS, are considered standard for evaluation of an antipsychotic compound in a population with schizophrenia. The C-SSRS is commonly used for stringent monitoring of the risk for suicidality in clinical trials ([Posner et al, 2011](#)).

4.3 Justification for Dose

Emraclidine doses and dosing frequency in this trial are based on the safety/tolerability data and PK profile of emraclidine from Trials C2561001 and CVL-231-SCH-001. The targeted maximum dose level of 30 mg QD in this trial represents the top end of the therapeutic dose range for emraclidine. The emraclidine 30 mg QD dose demonstrated clinically meaningful and statistically significant antipsychotic activity compared with placebo as assessed by changes from Baseline at Week 6 in the PANSS total score in a Phase 1b trial in participants with an acute exacerbation of schizophrenia. emraclidine 30 mg QD, dosed for up to 6 weeks without titration, has been deemed safe and well tolerated in participants with schizophrenia. As mentioned above, this dose was associated with a maximum increase of 4.4 bpm in supine heart rate and 1.2 mmHg in supine systolic blood pressure (Week 6 average at 2 hours post morning dose compared with placebo).

The 15 mg QD dose is selected to understand the efficacy at a lower dose. Based on range of doses evaluated in the multiple ascending dose trial (CVL-231-SCH-001), the 15 mg QD dose is expected to be safe and well tolerated. The 2 doses of 30 mg QD and 15 mg QD will facilitate the evaluation of efficacy of emraclidine across a wide exposure range for a thorough understanding of exposure responsiveness of emraclidine effects.

4.4 End of Trial Definition

The end of the trial is defined as the date of the last visit (including follow-up safety contact) of the last participant in the trial globally.

The definition of a completed participant is provided in [Section 4.1.4](#).

5 TRIAL POPULATION

Men and women, 18 to 65 years of age, inclusive, with a primary diagnosis of schizophrenia who are experiencing an acute exacerbation or relapse of psychotic symptoms will be enrolled into the trial.

5.1 Inclusion Criteria

Individuals are eligible for participation in this trial only if all of the following criteria apply:

General	
1.	Male and female participants, ages 18 to 65 years, inclusive, at the time of signing the ICF.
Target Disease Characteristics	
2.	Primary diagnosis of schizophrenia per DSM-5, as confirmed by the MINI for Psychotic Disorders version 7.0.2.
3.	CGI-S ≥ 4 (moderately to severely ill) at the time of signing the ICF and Baseline.

4.	
PANSS Total Score between 85 and 120, inclusive, at the time of signing the ICF and at Baseline.
 
Additionally, participants must meet a score of ≥ 4 (moderate or greater) for ≥ 2 of the following Positive Scale items at the time of signing the ICF and at Baseline:
 
 • Positive Scale Item 1 (delusions) • Positive Scale Item 2 (conceptual disorganization) • Positive Scale Item 3 (hallucinatory behavior) • Positive Scale Item 6 (suspiciousness/persecution)
5.	
Experiencing an acute exacerbation or relapse of psychotic symptoms, with onset less than 60 days prior to signing the ICF.
 
 • Participant requires hospitalization for this acute exacerbation or relapse of symptoms • If participant is already an inpatient at the time of signing the ICF, has been hospitalized for ≤ 14 days for the current episode of psychosis at the time of signing the ICF, excluding hospitalization for psychosocial reasons
6.	
Scores as follows (normal to mild symptoms) at the time of signing the ICF and Baseline (Day 1):
 
 • All individual items of the SAS < 2 • All individual items (Items 1-7) of the AIMS < 2 • Clinical global assessment item of the BARS < 3
7.	
Willing to discontinue all prohibited medications to meet protocol-required washouts prior to and during the trial period.

8.	
Resides in a stable living environment as demonstrated by the ability to provide contact information for themselves and/or family/friend/caregiver.

Other and Administrative Criteria

9.	
Agree to comply with the following contraception requirements during the trial and for 7 days after the last dose of IMP:
 
 • Sexually active men must agree to use a condom and practice contraception during treatment and until the end of relevant systemic exposure (ie, 7 days after the last dose of IMP). • Sexually active women of childbearing potential must use highly effective contraception as defined in Section 10.4.1.1 
In addition, male participants should not donate sperm for a minimum of 7 days following the last dose of IMP.

10.	
Body mass index of 18.0 to 40.0 kg/m² and a total body weight ≥ 50 kg (110 lbs).

11.	
Capable of giving signed informed consent, which includes compliance with the requirements and restrictions listed in the ICF and in Section 10.1.3.

12.	
Ability, in the opinion of the investigator, to understand the nature of the trial, participate in trial visits, and comply with protocol requirements, including the prescribed dosage regimens, scheduled visits, laboratory tests, outcomes measures, and other trial procedures.

Abbreviations: AIMS=Abnormal Involuntary Movement Scale; BARS=Barnes Akathisia Rating Scale; CGI-S=Clinical Global Impression–Severity of Symptoms; DSM-5=Diagnostic and Statistical Manual of Mental Disorders, Fifth Edition; ICF=informed consent form; IMP=investigational medicinal product; MINI=Mini International Neuropsychiatric Interview; PANSS=Positive and Negative Syndrome Scale; SAS=Simpson Angus Scale.

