6. To address ICE of trial or treatment discontinuation with no outcome data collected post discontinuation, the primary analysis of MMRM described above will be followed by pattern mixture model (PMM) approach with varying level of shift parameters for missing values due to discontinuations that are potentially missing not at random (MNAR), including discontinuation due to lack of efficacy or due to adverse events. This will be implemented using delta adjustment imputation method. Further details will be described in the statistical analysis plan (SAP).

The statistical hypothesis testing on the primary endpoint (emraclidine 30 mg QD vs placebo and emraclidine 15 mg QD vs placebo) will be based on the estimated treatment difference from the model at Week 6 and will be tested in a hierarchical order with each at 2-sided alpha level 0.05. The evaluation of other time points will also be derived from the same model.

The number and proportion of responders (ie, participants with 30% reduction from Baseline in the PANSS total score at Week 6 or the last assessment before discontinuation) will be summarized. A logistic regression model, with baseline PANSS as a covariate, will be used to compare the proportion of responders in each active arm with placebo. If expected counts are <5, then a Fisher's Exact test will be used.

The secondary estimand has the following attributes:

1. Treatments as randomized
2. mITT population as the primary population of interest
3. Change from Baseline to Week 6 in CGI-S score as the endpoint of interest
4. The population level summary of interest is the treatment differences estimated based on the least square mean and the corresponding 95% confidence interval from the MMRM model with treatment, visit, and treatment by visit interaction as fixed effect, participant as a random effect, and baseline CGI-S score as a covariate. An unstructured covariance structure will be used for the repeated measures. If the unstructured covariance matrix results in convergence issue, the heterogeneous Toeplitz covariance structure followed by the heterogeneous first-order autoregressive (AR(1)) structure will be used. When a reduced covariance matrix is used, the sandwich variance estimator will be used. The Kenward-Roger approximation will be used to estimate the denominator degrees of freedom.
5. ICEs will be addressed using the same strategies as described above for the primary endpoint.

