9.5 Sample Size Determination

A sample size of approximately 93 participants in each treatment group completing the Week 6 assessments (approximately 279 in total) should provide at least 90% power to detect an effect size of 0.48 in change from Baseline in PANSS total score at Week 6 between either active treatment group versus placebo at the $\alpha=0.05$ level. The effect size of 0.48 represents a clinically meaningful effect on symptom reduction based on large scale meta-analysis of historical data from several currently approved antipsychotic medications in common usage ([Leucht et al, 2013](#)). It could be translated into a difference of 7 points versus placebo if the standard deviation of change from baseline is 14.6 points or a difference of 8 points versus placebo if the standard deviation of change from

baseline is 16.7 points. Both scenarios of the standard deviation are consistent with historical observations. To account for a discontinuation rate of approximately 25% for a 6-week treatment period (as observed in Trial CVL-231-SCH-001), it is planned to randomize approximately 372 participants.

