## 1.2. Sample Size Considerations

A sample size of approximately 93 subjects in each treatment group completing the Week 6 assessments (approximately 279 in total) should provide at least 90% power to detect an effect size of 0.48 in change from Baseline in the Positive and Negative Symptom Score (PANSS) total score at Week 6 between either active treatment group versus placebo at the  $\alpha=0.05$  level. The effect size of 0.48 represents a clinically meaningful effect on symptom reduction based on large scale meta-analysis of historical data from several currently approved antipsychotic medications in common usage ([Leucht et al, 2013](#)). It could be translated into a difference of 7 points versus placebo if the standard deviation of change from baseline is 14.6 points or a difference of 8 points versus placebo if the standard deviation of change from baseline is 16.7 points. Both scenarios of the standard deviation are consistent with historical observations. To account for a discontinuation rate of approximately 25% for a 6-week treatment period (as observed in Trial CVL-231-SCH-001), it is planned to randomize approximately 372 subjects.

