## 5.6. Subject Disposition, Demographic and Baseline Characteristics

Subject disposition will be based on the ITT population with tabulation of the number of subjects who complete the study and the number of subjects discontinued from the study and the reasons by treatment group. Additionally, the number of days on study will be summarized.

Further tabulation by region (United States, Other Countries) and country will also be presented. Subject disposition data will also be tabulated for all subjects screened to include the number of subjects screened, the number of screen failures, and the reason for screen failure.

Number of subjects in each analysis population set will be summarized.

Additionally, the number of subjects randomized at each site and overall will be summarized by country, treatment group, and overall. Summaries will be presented for randomized subjects and completed subjects.

Demographic data and baseline characteristics including age, age group, sex, fertility status, race, ethnicity, smoking status (smoker vs. non-smoker) at Baseline, height at screening, weight at screening and baseline, BMI at screening and baseline, will be summarized using descriptive statistics for the ITT population. Further tabulation by region and country also will be presented.

Baseline disease characteristics including time (years) since diagnosis of schizophrenia, number of hospitalizations in the last 5 years, PANSS total score at Baseline, PANSS positive subscale score at Baseline, PANSS negative subscale score at Baseline, PANSS Marder Negative score at Baseline, PANSS delusions score at Baseline, PANSS conceptual disorganization score at Baseline, PANSS hallucinatory behavior score at Baseline, PANSS suspiciousness/persecution score at Baseline, CGI-S score at Baseline, change in PANSS total score from Screening to Baseline (Screening – Baseline), and percent change in PANSS total score from Screening to Baseline will be summarized by treatment group. Further tabulation by region and country also will be presented.

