### **5.9.2. Main Analytical Approach**

The change from baseline to each study visit in total PANSS score will be summarized by visit and treatment group. A MMRM analysis will be used to analyze the data from all post-randomization timepoints up to Week 6 with treatment, geographic region, visit, and treatment by visit interaction as fixed effect, subject as a random effect, and baseline PANSS score as a covariate. An unstructured covariance structure will be used for the repeated measures. If the unstructured covariance matrix results in convergence issue, the heterogeneous Toeplitz covariance structure followed by the heterogeneous first-order autoregressive (AR(1)) structure will be used. The Kenward-Roger approximation will be used to estimate the denominator degrees of freedom. The difference between each emraclidine dose group and placebo at Week 6 will be estimated based on the Least Squares Mean (LSMean) difference between the treatment groups at Week 6 from the MMRM with the associated 95% confidence interval (CI) and P-value. A Cohen's D value will be derived as the ratio of the estimated difference to the population standard deviation at each visit estimated from the model (the square root of the diagonal elements of the estimated covariance matrix). The missing values are assumed to be missing at random for the main analysis, including missing due to missed visits or early termination due to COVID-19 control measures. The LSM ( $\pm$ SE) from the model will be plotted for change in PANSS total score by visit and treatment group. Similarly, the mean ( $\pm$ SD) of absolute values and change from Baseline PANSS total score will be presented by visit and treatment group.

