### **5.10.2. Main Analytical Approach**

Similar to the analysis of the primary efficacy variable, the change from baseline to each study visit in CGI-S score will be summarized by visit and treatment group. A MMRM analysis will be used with treatment, geographic region, visit, and treatment by visit interaction as fixed effect, subject as a random effect, and baseline CGI-S score as a covariate. An unstructured covariance structure will be used for the repeated measures. If the unstructured covariance matrix results in convergence issue, the heterogeneous Toeplitz covariance structure followed by the AR(1) structure will be used. The Kenward-Roger approximation will be used to estimate the denominator degrees of freedom. The difference between each emraclidine dose group and placebo at Week 6 will be estimated based on the LSMean difference between the treatment groups at Week 6 from the MMRM with the associated 95% CI and p-value. A Cohen's D value will be derived as the ratio of the estimated difference to the population standard deviation at each visit estimated from the model (the square root of the diagonal elements of the estimated covariance matrix). The missing values are assumed to be missing at random for the main analysis, including missing due to missed visits or early termination due to COVID-19 control measures. The LSM ( $\pm$ SE) from the model will be plotted for change in CGI-S score by visit and treatment group. Similarly, the mean ( $\pm$ SD) of absolute values and change from Baseline CGI-S score will be presented by visit and treatment group.

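### Free improvement: the Screening PANSS and CGI-S ratings could join Baseline as covariates in the primary and key secondary models, for a probably small gain in precision

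*Protocol*

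**What the plan says.** Protocol 5.1, criterion 4, requires "PANSS Total Score between 85 and 120, inclusive, at the time of signing the ICF and at Baseline". Criterion 3 sets a CGI-S minimum at the same two time points. The Schedule of Assessments lists both scales at Screening and Baseline, and Exclusion Criterion 4 (Protocol 5.2) compares the two PANSS totals.

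SAP 4.1.6 defines baseline as the most recent value before dosing, so Screening serves as baseline only if the Day 1 value is missing or was taken after dosing. SAP 5.5 enters that single value for each efficacy variable. The primary model (SAP 5.9.2) has treatment, region, visit and treatment by visit, with "subject as a random effect, and baseline PANSS score as a covariate". The key secondary model (SAP 5.10.2) is the same with "subject as a random effect, and baseline CGI-S score as a covariate". The PROC MI code in SAP 9.6.1 carries only the baseline score Y0 and the post-baseline scores.

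The Screening PANSS is used in the SAP only descriptively: SAP 5.6 tabulates the absolute change and "percent change in PANSS total score from Screening to Baseline". Neither document says why it is left out of the models.

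**The concern.** One PANSS rating measures a participant's severity with error. A second rating of the same scale, made before randomisation, can carry further information about the Week 6 score. If it does, leaving it out makes the Week 6 residual variance larger than it need be. Treatment cannot affect a pre-randomisation rating, so adding it does not bias the randomised comparison.

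What is at stake is precision on the four sequential tests in SAP 5.3 and 5.4. Each is reached only if every earlier one succeeds, so a smaller standard error helps at each step where Screening is informative.

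**Working it through.** **Inputs from the documents**
- Alpha: the two primary comparisons "will be tested in a hierarchical order with each at 2-sided alpha level 0.05" (Protocol 1.1), so each has full alpha.
- Size: "A sample size of approximately 93 participants in each treatment group completing the Week 6 assessments", which "should provide at least 90% power to detect an effect size of 0.48" (Protocol 9.5).
- Effect: a "difference of 7 points versus placebo if the standard deviation of change from baseline is 14.6 points" (SAP 1.2), or 8 points with SD 16.7. 7/14.6 = 0.479 and 8/16.7 = 0.479.
- Discontinuation 25%; 372 randomised.

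**Step 1: the plan's own figure**
- n per arm = 2(1.960 + 1.282)²/0.48² = 91.2, so 92. The exact noncentral t gives 93.
- Power at 93 = Φ(0.48·√(93/2) − 1.96) = Φ(3.273 − 1.96) = 90.5%. The noncentral t gives 90.3%.
- 93/0.75 = 124 per arm, and 3 × 124 = 372.

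The figure reproduces. It is based on the SD of change and takes no credit for covariate adjustment.

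**Step 2: what the Screening score can add**

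With Baseline already in the model, adding Screening multiplies the Week 6 residual variance by 1 − pr². Here pr is the partial correlation of Screening (S) with Week 6 given Baseline (B):

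pr = (r_S6 − r_B6·r_SB) / √[(1 − r_B6²)(1 − r_SB²)]

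Power becomes Φ(3.273/√(1 − pr²) − 1.96), taking 0.48 as the effect after baseline adjustment. The values of pr are assumed.

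| pr | Variance | SE | Power | Evaluable participants saved per arm (93·pr²) |
|---|---|---|---|---|
| 0 | 0 | 0 | 90.5% | 0 |
| 0.10 | −1.0% | −0.5% | 90.8% | 0.9 |
| 0.15 | −2.3% | −1.1% | 91.2% | 2.1 |
| 0.20 | −4.0% | −2.0% | 91.6% | 3.7 |
| 0.25 | −6.3% | −3.2% | 92.2% | 5.8 |

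For example, r_B6 = r_S6 = 0.4 with r_SB = 0.6 gives pr = 0.16/√(0.84 × 0.64) = 0.218: variance −4.8%, power 91.8%. If correlation only decays serially (r_S6 = r_B6·r_SB), the numerator and the gain are zero.

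**Step 3: simulation with the entry rules**

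Scores were generated with 85–120 required at both visits and less than 20% improvement between them. All SDs are assumptions. The reduction in Week 6 residual variance was:

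| SD: person / rating error / washout | Severity fully persists, washout shift vanishes | Both fully persist | Both half persist |
|---|---|---|---|
| 12 / 6 / 4 | about 6% | 2.8% | 0.8% |
| 8 / 4 / 4 | 4.6% | 1.2% | 0.3% |

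With no washout variation and half persistence the reduction is 0.6–1.1%. With no persistence it is zero. A reduction of 0.3–1.1% moves power from 90.5% to about 90.6–90.8%.

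**Step 4: the planned repeated-measures model**

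This check used eight assumed covariance structures, large samples and complete data.
- Adding Screening with a common slope gave a Week 6 variance 0.947 to 0.9998 of the planned model's. It was never larger.
- Letting both Screening and Baseline slopes vary by visit gave 0.940 to 0.980 of the planned model's. Under pure decay almost all of that came from freeing the Baseline slope, and Screening itself added almost nothing.

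**The case against.** The strongest case against is that nothing here is wrong. The plan adjusts for baseline and region, and it reaches its stated power without relying on any adjustment. That stands: this is an optional gain.

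The second objection concerns size. A reader might infer a dependable variance reduction of 2.4–5.8%, or 9–22 of the 372 participants. Those figures arise only if severity persists fully to Week 6 and washout variation disappears by then. The documents point away from the second condition: prior antipsychotics are washed out between the two ratings (Protocol 4.1.1), they stay prohibited during treatment (Table 5), and data after sustained antipsychotic use are censored (SAP 5.9.1). The off-drug Baseline state may therefore be closer to Week 6 than Screening is. This objection also stands, and it pulls the likely gain toward the lower part of the range.

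Two further inferences lack support. The PANSS figures cannot be carried over to CGI-S, a 7-point scale with entry at 4 or more, for which nothing was calculated. Nor is absorbing regression to the mean a separate benefit: it is balanced across randomised arms in expectation, and any precision it yields is the same variance reduction counted again.

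None of this removes the point. The score is already collected, and the cost of an uninformative covariate is about one degree of freedom per added term.

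**Conclusion.** The point holds as a free improvement of low priority. Two pre-dose ratings should exist on each scale for every eligible randomised participant, and only the last enters the primary and key secondary models.

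For PANSS, the expected gain is about 0–6% in Week 6 residual variance, or 0–3% in standard error, with power per comparison at 0.48 moving from 90.5% to at most about 92%. This rests on assumed partial correlations of 0 to 0.25. It is probably in the lower part of that range if severity only partly persists or washout changes carry through to Week 6, and it is zero if Screening adds nothing to Baseline. The CGI-S gain is unquantified.

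The documents do not support a reading that the trial is underpowered, that the planned tests are biased, or that the 93 per arm is wrong.

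**What to change.** Before unblinding:

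1. Add the Screening PANSS total to the model in SAP 5.9.2 and the Screening CGI-S to the model in SAP 5.10.2. Preferably let the Screening and Baseline scores each interact with visit, so that the adjustment applies at Week 6.
2. Add the same Screening score to the PROC MI VAR list in SAP 9.6.1, so that the imputation analyses match the main model.
3. State which Screening value is used. For a rescreened participant, who receives a new number under Protocol 5.4, it is the value from the screening episode that led to randomisation. Where Screening already serves as baseline under SAP 4.1.6, the same value is entered for both covariates.
4. Restrict the wording to PANSS total and CGI-S. SAP 5.13 and 5.15 reuse the 5.9.2 model for other endpoints, and some of these, such as BACS and SF-6D, have no Screening score.

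The cost is a few sentences in the SAP, a small change to the model and imputation code, and about one degree of freedom per added term. No new data, visits or participants are needed.
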